## **17. Exploratory Effectiveness Analyses on Monthly Measurements**

Monthly measurements of the secondary outcomes, including pain intensity, pain interference, and physical function, will be assessed by addressing (1) the trajectory of how long it takes until patients improve (i.e., demonstrate a 30% improvement) and (2) what proportion of people receiving acupuncture treatments improve at three months if they don't improve (30% improvement) after one or two months of acupuncture treatment. Address these questions will help understand how much acupuncture is needed to improve and at what time should acupuncture treatment stop if improvement is not observed by then, given each individual's outcome trajectory. We will examine individuals' longitudinal trajectory on the monthly measurements in the exploratory analyses. In addition, we will conduct exploratory per protocol analyses assessing dose response to evaluate

the impact of numbers of received acupuncture treatments on improving the secondary outcomes. The UMC group will be included with their numbers of received treatments assigned as 0 in the analyses.

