The PROMIS®, the Patient-Reported Outcomes Measurement Information System, was developed as a set of patient reported outcomes that can assess physical, mental and social health in adults and children.^{76,77} In this study, we propose to use four domains of the PROMIS®-29, which has eight outcome domains important for a study of CLBP in older adults. These include physical function, sleep disturbance, fatigue and ability to participate in social roles. All short-form measures we will use are 4-items except for Physical Function. The RTF recommends the use of pain intensity, pain interference, physical function, depression, anxiety, and sleep disturbance, all domains covered by the PROMIS®-29.⁶⁰ Deyo et al.⁷⁸ found that the PROMIS®-29 measures had good to excellent internal consistency and worse scores among older patients with chronic pain associated with falls, high catastrophizing and worker's compensation, suggesting its value for use with older adults. Hence, we believe the PROMIS measures are best suited for use with our older adult population. However, in the interest of adopting all the required HEAL CDEs, we will add 2-items to the physical function and sleep disturbance questions so that they are the 6-item HEAL core recommended versions of these scales, and substitute the PHQ-4 anxiety depression screener rather than use the PROMIS® anxiety and depression scales. All versions of the multi-item short-forms we are using include the range of mild to severe impairment for that domain and measure at least 3 standard deviations of the T-scores⁸⁰, the healthy population plus roughly two standard deviations of the unhealthy population.⁸¹ Correlations between each multi-item short form we are using and the

full-item bank are above 0.9 for all domains except physical function, where the correlation is roughly 0.87.⁸⁰ Power for detecting a small (0.2) effect in a clinical population for each multi-item measure with our sample sizes is well over 90%.⁸⁰ Construct validity was demonstrated for these measures as well.⁸⁰ Below, we describe other features of the individual PROMIS® short form measures we are using.

Physical Function will be measured by the 6-item PROMIS® physical function measure. It has been found to perform well psychometrically compared to the RMDQ.⁸⁴ It is a secondary outcome.

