6.2.4 Follow-up Assessments

Each participant will be followed for 12-months post-randomization. Participants will be invited to complete short monthly check-ins per their preferred mode (phone or web) between main assessments at 3-, 6- and 12-months. Monthly check-ins will take less than 5-minutes to complete and will be limited to administration of the PROMIS® Physical Function (6-items) and PEG (3-items). Participants will receive a \$5 incentive for each check-in completed typically payable as a lump sum at the end of the study (up to \$45 total for the 9 monthly check-ins). Patients will be contacted via their preferred mode (phone or web) for the 3-, 6-, and 12-month follow-up surveys. Advance letters will be mailed as reminders to those preferring phone follow-up and emails with the reminder and a live hyperlink will be sent to those preferring to complete follow-ups online. Participants may opt to change their preferred mode at any time. Incentive payments of \$20, \$25 and \$30 will be sent for completing 3-, 6- and 12-month follow-ups, respectively.

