## 14. Effectiveness Analyses on Secondary Outcomes

Secondary outcomes including the PEG, patient global impression of change for pain, and physical function will be evaluated at 3-, 6-, and 12-months post randomization by comparing the measurements at the three time points to the baseline. We will follow similar framework as described above for RMDQ scores to analyze the effectiveness of acupuncture treatments, SA and EA, on the secondary outcomes. In addition, the occurrence of an  $\geq 30\%$  improvement in RMDQ and PEG measures at 3-, 6-, and 12-months compared to the baseline will be evaluated under the same framework. A link function will be chosen appropriately for each outcome.

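### SAP 17 applies a 30% relative improvement to PROMIS physical function without stating how that scale is scored, so who counts as improved depends on the scoring origin and the baseline level

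*SAP*

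**What the plan says.** SAP 17 opens: "Monthly measurements of the secondary outcomes, including pain intensity, pain interference, and physical function, will be assessed". It then asks two questions. The first concerns "the trajectory of how long it takes until patients improve (i.e., demonstrate a 30% improvement"). The second asks what proportion of people receiving acupuncture "improve at three months if they don't improve (30% improvement) after one or two months of acupuncture treatment". The same 30% definition serves both questions, and no measure is exempted. The section says the answers will help show how much acupuncture is needed and "at what time should acupuncture treatment stop if improvement is not observed by then".

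Protocol 6.2.4 says the monthly check-ins are "limited to administration of the PROMIS® Physical Function (6-items) and PEG (3-items"). Physical function is therefore one of two monthly instruments.

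Elsewhere the 30% criterion is narrower. The secondary outcome table in SAP 2.2 has 30% responder rows for RMDQ and PEG and lists physical function only as a continuous change. SAP 14 likewise evaluates a 30% "improvement in RMDQ and PEG measures at 3-, 6-, and 12-months compared to the baseline". Protocol 9.5.2 names RMDQ and pain intensity, not function. Protocol 9.6 describes the monthly questions without defining improvement.

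On scoring, SAP 2.2 refers only to scores from the PROMIS physical function subscale. Protocol 6.2.2 mentions T-scores when it describes the range of the short forms, which "measure at least 3 standard deviations of the T-scores". Neither document says which metric will be analysed.

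**The concern.** A percentage change makes sense when zero means none of the problem. PEG meets that condition: SAP 2.2 gives it as the average of three items scored 0 to 10. A T-score has a conventional origin, and a sum of six items scored 1 to 5 starts at 6. On either metric the percentage depends on where the scale happens to begin.

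If higher scores mean better function, the rule also sets a bar of 0.3 times the baseline score, so less disabled patients must gain more points to count as improved. Time to improvement and the share of late improvers, when read on function, would then partly reflect the scoring convention and the baseline level. SAP 17 means to draw conclusions from those results about how much treatment is needed.

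**Working it through.** The documents state no responder rate, power or sample size for a 30% gain in function, so there is no figure of the plan's own to reproduce. They also give no baseline mean, baseline SD or change SD for this scale. Everything numerical below is therefore an assumption unless marked otherwise.

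**Assumed metrics.** (a) T-score with population mean 50, SD 10, higher = better. (b) Raw sum of six items scored 1 to 5, range 6 to 30, higher = better. The six items are from SAP 2.2.

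**Step 1. Required gain on the T-score.** Required gain = 0.30 × baseline.

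| Baseline T | Gain needed | In population SDs (÷ 10) |
|---|---|---|
| 25 | 7.5 | 0.75 |
| 30 | 9.0 | 0.90 |
| 35 | 10.5 | 1.05 |
| 40 | 12.0 | 1.20 |
| 45 | 13.5 | 1.35 |
| 50 | 15.0 | 1.50 |

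The bar doubles between 25 and 50.

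**Step 2. Required gain on the raw sum.** The target is 1.3 × baseline. At 23 it is 29.9, so 30 is needed (+7). At 24 it is 31.2, above the maximum of 30. The cut-off is 30/1.3 = 23.1, so 30% is unreachable from 24 up.

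**Step 3. Dependence on the origin.** Take a patient who moves from 18 to 22 on the 6-30 sum. The gain is 4/18 = 22%, not improved. Subtract 6 from every score so that the scale runs 0 to 24. The same answers now move from 12 to 16, and 4/12 = 33%, improved. The patient's answers are unchanged; only the constant has moved.

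**Step 4. Same benefit, different baseline.** Give every patient the same distribution of true T-score change, mean 3 and SD 6. Then P(improved) = Φ((3 − 0.3 × baseline)/6).

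- Baseline 25: Φ(−4.5/6) = Φ(−0.75) = 23%
- Baseline 35: Φ(−7.5/6) = Φ(−1.25) = 11%
- Baseline 50: Φ(−12/6) = Φ(−2.00) = 2%

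**Step 5. Overall share reaching 30% on T-scores.** With baseline B and change C independent,

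P = Φ((mean C − 0.3 × mean B) / √(Var C + 0.09 × Var B)).

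The baseline SD is 7, the baseline mean 30 to 45, the mean change 1 to 6 and the change SD 5 to 10.

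- Lowest: B 45, C 1, SD 5. (1 − 13.5)/√(25 + 4.41) = −12.5/5.42 = −2.31, giving 1%.
- Highest: B 30, C 6, SD 10. (6 − 9)/√(100 + 4.41) = −3/10.22 = −0.29, giving 38%.
- Middle (B 35 to 40, C 2 to 4, SD 5 to 8): from −10/5.42 = −1.84, or 3%, to −6.5/8.27 = −0.79, or 22%.

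A correlation of −0.35 between change and baseline raises the top of the range to 39%. A simulation on the raw sum (baseline mean 14 to 20, SD 4.5; mean change 1 to 3, SD 3 to 5; correlation 0 or −0.35) gave about 6% to 42%.

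**Step 6. What a half-SD rule would do instead.** With an assumed baseline SD of 5.5 the threshold is 2.75 points. At zero mean change, the share crossing it at any one month is Φ(−2.75/5) = Φ(−0.55) = 29% for a change SD of 5, and Φ(−2.75/6) = Φ(−0.46) = 32% for a change SD of 6. Repeated monthly looks would push the share that ever crosses higher.

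**The case against.** The strongest reply has four parts.

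First, the SAP never says it will analyse T-scores. The protocol mentions them only when describing how the short forms perform. This stands, and it is why both metrics above are labelled as assumptions. It does not remove the problem, because the six-item raw sum has no zero either and the metric is left unstated.

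Second, a reader might infer from Step 1 that almost nobody could improve on function. The documents do not support that. They give neither the baseline distribution nor the variability of change, and near-zero rates appear only in one corner of the assumed range.

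Third, a reader might infer that better-functioning patients will be reported as least responsive, or that one arm will be favoured. SAP 17 plans no comparison by baseline function, and the baseline moderator in SAP 15.1 concerns RMDQ change at 6 months. One threshold applied to all randomised arms does not by itself favour any of them. This part stands.

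Fourth, function is not reported only through the 30% cut. SAP 2.2 lists its monthly measurements under a continuous outcome, and SAP 17 also plans to examine individual trajectories. PEG can answer both questions on its own. This limits the damage but leaves the stated definition of improvement in force for function.

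**Conclusion.** The point holds as a defect of definition. SAP 17 applies a 30% relative criterion to a scale for which the SAP uses it nowhere else, and it does not state the metric. That the percentage depends on the scoring origin follows from arithmetic on either assumed metric. That the bar rises with baseline follows too, provided higher means better.

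The effect on responder rates is not established. About 1% to 38% on T-scores is a range over assumed inputs and says mainly that the result cannot be interpreted until the metric is fixed.

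Severity is minor. Protocol 9.5.3 treats the monthly measurements as tertiary and exploratory. Physical function at 3, 6 and 12 months is analysed as a continuous change, and the primary and secondary results are unaffected.

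**What to change.** In SAP 17:

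- Limit the 30% rule to PEG.
- State the physical function metric and its direction.
- Make the mean trajectory by arm, on the continuous score, the main analysis of monthly function.
- If a responder cut is still wanted for function, prespecify one absolute-change threshold with its justification, before unmasking.
- If that threshold is distribution-based, such as half the baseline SD, report the UMC rate beside it. About 30% could cross it at any month with no mean change (Step 6), and without the UMC rate that fluctuation could be read as improvement.

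The cost is SAP wording only; no new data are needed. What is given up is a single definition of improvement shared by both monthly instruments.

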Stakeholder participants will be invited for a 30-45 minute interview. Phone interviews will be recorded via Teams. The recording will begin after the interviewer briefly reviews the information sheet with the stakeholder participant to respond to any questions, and after the participant gives verbal consent to participate in the interview and be recorded (if the individual consents to the interview but not to be recorded, the interviewer will take notes to capture as much of the interviewee's responses as possible). The KPWHRI or KPNW staff performing the interview will take notes and will make a note in the REDCap database indicating whether the participant gave verbal consent to both participate and record the interview. If the interview is performed at KPNW, the recording will be sent to KPWA via secure file transfer for transcription.

The recording will be sent to a professional transcriptionist (Jackson Street Associates), with whom we have a Business Associate Agreement established, via secure file transfer to be transcribed. Interview transcripts will be returned to the study team via secure file transfer and stored in a secure project folder on the KP Washington network. Only BackInAction study staff will have access to the transcripts and will remove any identifiable information from the final transcripts. The audio files will be destroyed 5 years after the conclusion of the project.

Study staff will send an incentive of \$50 with a gift card to the stakeholder participant, if they are eligible to receive incentives, after completion of the interview.

Randomization

Patients will be randomized just after the baseline assessment has been completed. It is our intent that the baseline assessment is completed within a week of the eligibility screen (otherwise, back pain eligibility questions will need to be reassessed). Participants will receive \$15 for completion of the baseline assessment. Participants are asked to make their first visit to acupuncture within 10 days of being randomized.

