We will conduct a similar analysis for secondary and tertiary outcomes, including key secondary outcomes such as the PEG and will use appropriate link functions for non-continuous outcomes. All models will adjust for baseline outcome value, age, sex, and HCS as well as any baseline variables that are predictive of loss to follow-up. All analyses will be conducted following an intent-to-treat approach, including all individuals randomized regardless of their engagement with, or exposure, to the intervention. If loss to follow-up is above 15%, we will employ imputation techniques to address missing data issues.¹⁰⁴ However, our focus will be on minimizing loss to follow-up and in our collective substantial experience conducting similar trials, we have consistently had retention in line with this. The imputation method that we were referencing uses a pattern mixture approach that relaxes the missing at random assumption. This approach that we propose using is derived for GEE and is sensitive to potential non-ignorable missingness.¹⁰⁴

Exploratory analyses will further use tertiary outcome data collected monthly (i.e., the PEG and PROMIS®, Physical Function). We will use these measures to assess the trajectory of how long it takes until patients improve and to address questions such as “What proportion of people improve at three months if they don’t improve after one or two months of acupuncture?” These exploratory analyses will help address how much acupuncture is needed to improve and at what time, given a patient’s outcome trajectory, should acupuncture treatment stop if improvement has not been shown up to that time.

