The above power calculation was conducted with RMDQ score as the outcome. When the outcome of interest is the change on RMDQ score from baseline to 6-month, we expect a smaller SD than 6 points in each arm (based on previous trial data conducted at KPWHRI only the SD RMDQ at 6 months was 5.42 and change in RMDQ was 5.11). Thus, we are sufficiently powered ( $\geq 90\%$ ) to detect MCID differences between all pairwise group comparisons. Power was calculated via simulation using R software version 3.6 accounting for multiple comparisons of the three study arms using Fisher's Least significant different approach. Note to be conservative we assumed a larger SD than we expect since we may have loss to power due to clustering of participants within acupuncture provider (acupuncturists may see 10-15 participants) and we may have more variability in baseline outcome since this trial is pragmatic across four health care systems. Inflating the SD by more than 15% ( $6/5.11=1.17$ ) should take into account both potential loss to power issues. Furthermore, although acupuncturists may see up to 10-15 participants at our smallest site (IFH) this accounts for 16% of our expected recruited sample (123 of 789 with only two-thirds of those randomized to an acupuncture arm where clustering is of issue). At other sites, the combination of HCS embedded and community acupuncturists are expected to result in much smaller caseloads (3-8 participants on average). In keeping with a pragmatic trial approach and to lower barriers to participant receipt of acupuncturists, we are motivated to include a larger number of acupuncturists serving participants in the study

For any two group comparisons, given our sample size of 210 per group and a SD of 6, the 95% CI width around the difference in means between groups is +/- 1.15 pts. Further, for secondary analysis for the binary outcome 30% improvement in RMDQ from baseline we have >90% power to detect an MCID assuming the probability of improvement in UMC was between 33%  and 44%  and the MCID was a 15% improvement above UMC for each of the acupuncture groups. We will use an intent-to-treat approach in which participants will remain as randomized regardless if they withdrawal from treatment or cross-over to other treatment arm (e.g. UMC participant seeks acupuncture outside of study).

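### The late-improvement proportion meant to inform when acupuncture should stop (SAP 17, question 2) has no usual-care counterpart

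*SAP*

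**What the plan says.** SAP 17 sets two questions for the monthly PEG and physical function scores. Question (1) is "the trajectory of how long it takes until patients improve (i.e., demonstrate a 30% improvement"), with no arm named. Question (2) is "what proportion of people receiving acupuncture treatments improve at three months if they don't improve (30% improvement) after one or two months of acupuncture treatment". The stated use of the answers is to learn "how much acupuncture is needed to improve and at what time should acupuncture treatment stop if improvement is not observed by then".

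Protocol 9.6 puts question (2) in nearly the same terms, again conditional on one or two months of acupuncture, and gives the same purpose: "These exploratory analyses will help address how much acupuncture is needed to improve and at what time" treatment should end when improvement has not appeared.

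UMC comes into SAP 17 only after a new start: "In addition, we will conduct exploratory per protocol analyses assessing dose response to evaluate" the effect of the number of treatments. There UMC is coded as 0 treatments. Protocol 9.6 confirms the placement, because it has the zero coding inside the dose-response sentence itself.

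Two other places bear on the point. Protocol 6.2.4 invites participants to the monthly check-ins with no restriction by arm. SAP 4 powers the 30% RMDQ responder outcome "assuming the probability of improvement in UMC was between 33" and 44 percent, with acupuncture 15 points higher.

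**The concern.** Question (2) is the one that bears on stopping, and its answer is a one-arm proportion. Patients who have not improved at months 1 and 2 can improve at month 3 for reasons other than continued needling. Chronic low back pain varies: Protocol 7.2 treats a rise in back pain as expected natural variation. Patients enter on a symptom threshold (PEG general activity of at least 3), and they have access to usual care throughout. The proportion would therefore be above zero even if acupuncture did nothing.

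A reader given that proportion next to the stated purpose would naturally take it as the yield of carrying on. In question (2) that reading favours continued treatment. Protocol 2.2 says the trial should guide Medicare and the physicians and patients who choose a course of treatment, so a figure on treatment length is likely to be noticed even if it is labelled exploratory.

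**Working it through.** **Reading check.** Could the UMC sentence in SAP 17 cover question (2)? It could not. The sentence follows the dose-response analysis, and Protocol 9.6 ties it there. Dose response relates outcome to the number of treatments and does not condition on early non-improvement. The dose and adherence analyses in SAP 15.2 do not condition on it either. No passage gives question (2) a comparator.

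**Size.** The plan states no figure for this quantity, so there is none to reproduce. What follows is an illustration.

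Inputs from SAP 4:
- The UMC 30% responder rate is 33% or 44%. This is an RMDQ rate.
- Acupuncture is 15 points higher: 33 + 15 = 48% and 44 + 15 = 59%. This is applied at month 3.

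Assumptions not in the documents:
- The RMDQ rates hold for the monthly PEG and physical function scores.
- UMC rates at months 1/2/3 are 25/30/33% (low) or 33/40/44% (high).
- Within-person correlation r is between 0.5 and 0.8.
- Acupuncture rates at months 1 and 2 are either (a) UMC plus 15 points each month, giving 40/45/48% or 48/55/59%, or (b) UMC scaled in proportion to reach 48% or 59% at month 3.

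Model: L_m = √r·u + √(1−r)·e_m, with u and e_m independent standard normal. A patient is improved at month m if L_m < Φ⁻¹(p_m). The target is P(improved at 3 | not improved at 1 and not improved at 2), simulated with 2,000,000 draws.

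| r | UMC rates | UMC | Acupuncture (a) | Acupuncture (b) | UMC ÷ acupuncture, (a) / (b) |
|---|---|---|---|---|---|
| 0.5 | low | 18.9% | 26.4% | 27.4% | 0.72 / 0.69 |
| 0.5 | high | 25.1% | 33.1% | 34.3% | 0.76 / 0.73 |
| 0.8 | low | 11.4% | 15.5% | 17.0% | 0.74 / 0.67 |
| 0.8 | high | 15.5% | 20.3% | 22.1% | 0.76 / 0.70 |

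UMC runs from 11% to 25% and acupuncture from 16% to 34%. The UMC figure is two-thirds to three-quarters of the acupuncture figure. If acupuncture had no effect, the planned proportion would equal the UMC column. When the condition is non-improvement at month 1 only, the UMC figure is 18-33%.

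With a wider set of assumptions (r from 0.5 to 0.85, responder rates flat over the three months or rising as 60%, 80% and 100% of the month-3 rate), UMC is 7-27%, acupuncture is 10-38%, and the difference is 3-11 points.

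**Does the difference then answer the stopping question?** Take an early-acting treatment with 48% improved at every month, against UMC at 15/25/33%. The month-3 benefit is 48 − 33 = 15 points. The conditional proportions are 24.1% against 21.8% at r = 0.5 (+2.3 points) and 12.4% against 15.5% at r = 0.8 (−3.1 points). The difference nearly vanishes although the benefit is real, because the patients left in each arm as early non-improvers have been selected differently.

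**The case against.** The strongest defence is about status. Monthly measures are tertiary (Protocol 9.5.3), the analysis is labelled exploratory, no decision rule is set, and the wording is only that results will help understand the question. The share of early non-improvers who later improve under treatment is a legitimate descriptive figure. All of this stands, and it limits the weight of the point. It does not supply the missing background rate for a figure whose stated use is to inform stopping.

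Five stronger readings are tempting, and the documents do not support them.

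- *That the monthly analysis as a whole ignores UMC.* Only question (2) is restricted to acupuncture. Question (1) says patients, and the dose-response part includes UMC and bears on how much acupuncture is needed.
- *That the error always pushes toward more sessions.* That fits question (2). In question (1), background improvement would make acupuncture seem to work sooner, which points the other way.
- *That the plan itself explains UMC improvement by fluctuation or selection at entry.* SAP 4 gives planning rates without a reason, and UMC patients also receive active care.
- *That one month of acupuncture may be only about 20 days.* Protocol 6.2.2 says "Participants are asked to make their first visit to acupuncture within 10 days of being randomized". That is a request, so it gives no bound in either direction.
- *That a UMC column would settle when to stop.* It would not. The comparison conditions on an outcome after randomization, no arm is randomized to stop at month 1 or 2, and the early-acting example shows how the difference can mislead.

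**Conclusion.** The point holds for SAP 17 question (2) and its match in Protocol 9.6. As planned, the late-improvement proportion comes from acupuncture recipients alone and would be above zero with no acupuncture effect, so it overstates what continued acupuncture adds. In the illustration about 11-25% of UMC early non-improvers improve late, against about 16-34% with acupuncture, so most of the late improvement would also be seen under usual care.

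The direction is firm: the UMC share was not negligible in any scenario run. The size is not firm. It rests on RMDQ rates borrowed for measures that have no stated responder rate, and on assumed month-1 and month-2 rates and correlation. The analysis is exploratory, and the primary result is unaffected.

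**What to change.** In SAP 17 question (2) and the matching text of Protocol 9.6:

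1. Compute the same conditional proportions in UMC from its monthly PEG and physical function scores (not improved at month 1; not improved at months 1 and 2), and report the acupuncture-minus-UMC difference with a confidence interval.
2. State that the comparison is descriptive, because it conditions on non-improvement after randomization and no arm is randomized to stop at month 1 or 2.
3. State that no conclusion about when to stop will rest on the acupuncture-only proportion, or on the difference alone.

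Counting months from the first treatment is at most an optional sensitivity analysis.

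The cost is one more column and a difference in an exploratory table, plus two sentences of text. The data are already planned in all arms, and no study procedure changes. This point proposes no clinical stopping rule.
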